# 2. AIMS AND OBJECTIVES

# 2.1. Trial Objectives

# 2.1.1. Aims and Objectives

#### Aim

To investigate the clinical and cost-effectiveness of letrozole versus clomifene with or without metformin for ovulation induction in women with PCOS and infertility.

# 2.1.1 Primary Objective

To test the hypothesis that in women with PCOS and infertility, letrozole plus metformin versus clomifene plus metformin increases the live birth rate (≥ 34 weeks of gestation) by at least 10%.

# 2.1.2. Secondary Objectives

• To compare the paired drug effectiveness in women with anovulatory PCOS and infertility on live birth rate (≥ 34 weeks of gestation).

# **Objectives**

Letrozole vs clomifene

To compare the effectiveness of letrozole vs clomifene in women with anovulatory PCOS and infertility on live birth rate ( $\geq$  34 weeks of gestation).

Metformin vs Placebo

To compare the effectiveness of metformin vs placebo in women with anovulatory PCOS and infertility undergoing ovulation induction on live birth rate ( $\geq$  34 weeks of gestation).

Letrozole plus metformin vs clomifene plus metformin

To compare the effectiveness of letrozole plus metformin vs clomifene plus metformin in women with anovulatory PCOS and infertility on live birth rate (≥ 34 weeks of gestation).

 LOCI PROTOCOL
 Sponsor's reference: RG\_18-272
 v1.0 07-Nov-2019
 Page 20 of 57

 IRAS ID: 257918
 EudraCT number: 2018-004641-16
 ISRCTN: TBC

- Collect key secondary data on:
  - (i) Pregnancy loss (defined as pregnancy loss before 24 weeks of gestation)
  - (ii) Number of ovulation induction cycles to live birth
- Collect exploratory secondary data on:
  - (i) Treatment outcomes
  - (ii) Pregnancy end outcomes
  - (iii) Where live birth ≥24 weeks: gestational characteristics
  - (iv) Antenatal Outcomes
  - (v) Intrapartum Outcomes
  - (vi) Post-partum outcomes
  - (vii) Maternal outcomes
  - (viii) Neonatal outcomes
  - (ix) Survival at 28 days of neonatal life
  - (x) Heath economic evaluation: Hospital resource use and EQ-5D-5L questionnaire
- Collect Safety outcomes data
  - (i) Neonatal congenital or chromosomal abnormalities
  - (ii) Maternal adverse events
  - (iii) Multiple pregnancies
  - (iv) Ectopic pregnancies
  - (v) Ovarian hyperstimulation syndrome (OHSS)
  - (vi) Serious adverse events

# 2.1.3. Economic Aims and Objectives

To assess the cost-effectiveness of letrozole and the added value of metformin in the management of ovulation induction for women with PCOS and infertility based on an outcome of cost per additional live birth at  $\geq$  34 weeks of gestation from an NHS and personal social service (PSS) perspective. A secondary analysis reporting results in terms of cost per quality-adjusted life year (QALY) will also be carried out.

# 3. TRIAL DESIGN AND SETTING

#### 3.1. Trial Design

A 2x2 factorial randomised, double-blind, placebo-controlled multi-centre superiority trial of investigational medicinal products, with health economic evaluation and a six month internal pilot to ensure ability to recruit and randomise.

 LOCI PROTOCOL
 Sponsor's reference: RG\_18-272
 v1.0 07-Nov-2019
 Page 21 of 57

 IRAS ID: 257918
 EudraCT number: 2018-004641-16
 ISRCTN: TBC

# 3.2. Trial Setting

Approximately 45 gynaecology departments and/or fertility centres in the United Kingdom.

# 3.3. Identification of participants

Potential participants will be identified and approached by clinic doctors, nurses, research nurses and research midwives, after having received appropriate training relating to the trial. Recruitment will take place in gynaecology clinics and fertility clinics located across the United Kingdom.

The participant eligibility pathway to recruitment and randomisation is illustrated by the trial flowchart. They will be advised that participation in the study is entirely voluntary with the option of withdrawing from the study at any stage, and that participation or non-participation will not affect their usual care. Potential participants will be provided with a Study Participant Information Sheet (PIS) and given time to consider their involvement.

Eligible women will be given the opportunity to decide if they wish to participate, or if they need more time to consider their decision, or if they do not wish to participate. In all three scenarios, the decision of the woman will be respected. If a woman needs more time to consider her potential involvement, she will be asked to call the research nurse or midwife when she has decided. If an undecided woman does not call within 1 week, then the research nurse or midwife will contact her. If an initially undecided woman decides to participate later, the research nurse or midwife will arrange a mutually convenient opportunity for the woman to be consented, providing she still meets the eligibility criteria.

Women who give consent will proceed to randomisation if they are eligible to participate in the trial. Consent will be recorded on the approved consent form, which must be retained in the site file with a copy given to the participant and a copy sent to the LOCI Trial Office.

# 3.4. Assessment of Risk

All clinical trials can be considered to involve an element of risk and, in accordance with Birmingham Clinical Trials Unit (BCTU) operating procedures this trial has been risk assessed, to clarify any risks relating uniquely to this trial. This risk assessment concluded that the risk of participating to this trial is no higher than the risk of standard medical care and is there a Type A trial in accordance with risk-adapted approach to CTIMPs.

# 4. ELIGIBILITY

## 4.1. Inclusion Criteria

Women diagnosed with PCOS (according to Rotterdam criteria) and evidence of anovulation (anovulation is defined as irregular cycles lasting <21 or more than 35 days or less than 8 periods per year OR absence of raised serum progesterone greater than 20nmol/l 7 days prior to a period);

Presentation with infertility or wishing to conceive;

 LOCI PROTOCOL
 Sponsor's reference: RG\_18-272
 v1.0 07-Nov-2019
 Page 22 of 57

 IRAS ID: 257918
 EudraCT number: 2018-004641-16
 ISRCTN: TBC

- Male partner with normal sperm count (≥ 15 million) and progressive motility (≥ 32%) in the last 3 years;
- Willing and able to give informed consent.

#### 4.2. Exclusion Criteria

- Age ≤18 or ≥43 years at randomisation;
- Body Mass Index ≥35;
- Three or more previous ovulation induction treatments with either letrozole or clomifene;
- Currently on metformin treatment or inositol supplements for ovulation induction or for other indications
- Women opting for alternative methods of ovulation induction or treatment (GnRH agonists and antagonists, gonadotropins), triggering ovulation with hCG, or performing intrauterine or intracervical insemination;
- Contraindications to letrozole, clomifene, metformin use and/or pregnancy (see section 7.3 for full details on contraindications).
- Woman has previously participated in the LOCI trial.

#### 4.3. Co-enrolment

Co-enrolment may be permissible, but in all instances the recruiting centre should contact the LOCI Trials Office prior to offering the other trial.

# 5. CONSENT

It will be the responsibility of the Investigator to obtain written informed consent for each participant prior to performing any trial related procedures. A research nurse, research midwife or clinician is able to take consent providing that local practice allows this and responsibility has been delegated by the Principal Investigator as captured on the Site Signature and Delegation Log.

A Participant Information Sheet (PIS) will be provided to facilitate this process. Investigators, or delegates, will ensure that they adequately explain the aim, trial intervention, anticipated benefits and potential hazards of taking part in the trial to the participant. They will also stress that participation is voluntary and that the participant is free to refuse to take part and may withdraw from the trial at any time. The participant will be given an appropriate amount of time to read the PIS and to discuss their participation with others outside of the site research team. The participant will be given the opportunity to ask questions. If the participant expresses an interest in participating in the trial they will be asked to sign and date the latest version of the Informed Consent Form (ICF). The participant must give explicit consent for the regulatory authorities, members of the research team and/or representatives of the sponsor to be given direct access to the participant's medical records.

The Investigator, or delegate, will then sign and date the ICF. A copy of the ICF will be given to the participant, a copy will be filed in the medical notes, and the original placed in the Investigator Site File (ISF). Once the participant is entered into the trial, the participant's trial number will be entered on the ICF maintained in the ISF. In addition, if the participant has given explicit consent a copy of the signed ICF will be sent to the BCTU trials team for review.

 LOCI PROTOCOL
 Sponsor's reference: RG\_18-272
 v1.0 07-Nov-2019
 Page 23 of 57

 IRAS ID: 257918
 EudraCT number: 2018-004641-16
 ISRCTN: TBC

Details of the informed consent discussions will be recorded in the participant's medical notes. This will include date of discussion, the name of the trial, summary of discussion, version number of the PIS given to participant and version number of ICF signed and date consent received. Where consent is obtained on the same day that the trial related assessments are due to start, a note should be made in the medical notes as to what time the patient was approached about taking part in the trial, the time consent was obtained and what time the procedures started.

At each visit the participant's willingness to continue in the trial will be ascertained and documented in the medical notes. Throughout the trial the participant will have the opportunity to ask questions about the trial. Any new information that may be relevant to the participant's continued participation will be provided. Where new information becomes available which may affect the participants' decision to continue, participants will be given time to consider and if happy to continue will be re-consented. Re-consent will be documented in the medical notes. The participant's right to withdraw from the trial will remain.

Electronic copies of the PIS and ICF will be available from the Trials Office and for UK trials will be printed or photocopied onto the headed paper of the local institution. Details of all participants approached about the trial will be recorded on the Participant Screening/Enrolment Log and with the participant's prior consent, their General Practitioner (GP) will also be informed that they are taking part in the trial.

#### 6. ENROLMENT AND RANDOMISATION

# 6.1. Enrolment and Screening

The medical records of potential participants will be screened for eligibility by clinic doctors, nurses, research nurses and research midwives, after having received appropriate training relating to the trial. Clinic doctors will confirm eligibility for the trial.

# 6.2 Randomisation

## 6.2.1. Randomisation Methodology

Participants will be randomised on-line via a secure internet facility at the level of the individual in a 1:1 ratio to either letrozole or clomifene and at the same time randomised to metformin or placebo.

A minimisation algorithm will be used within the online randomisation system to ensure balance in the treatment allocations (both randomisations will occur simultaneously effectively resulting in four allocation groups) over the following variables:

- maternal age (<35 and ≥35 years);

- body mass index (<30 and ≥30);

- any previous pregnancy (yes and no)
- previous exposure to either clomifene or letrozole;
- any periods in the preceding 6 months (yes and no)
- randomising centre

 LOCI PROTOCOL
 Sponsor's reference: RG\_18-272
 v1.0 07-Nov-2019
 Page 24 of 57

 IRAS ID: 257918
 EudraCT number: 2018-004641-16
 ISRCTN: TBC

A 'random element' will be included in the minimisation algorithm, so that each participant has a probability (unspecified here), of being randomised to the opposite treatment that they would have otherwise received.

Full details of the randomisation specification will be stored in a confidential document at BCTU.

# 6.2.2. Blinding

This trial will be double-blinded, with over-encapsulation of the letrozole and clomifene and a matched placebo controlled IMP for metformin. Dose escalations for letrozole and clomifene will be identical in terms of the number of tablets the patient has to take in each cycle (e.g. month one = 1 tablet, month two = 2 tablets, month three = 3 tablets) therefore, the blinding will be maintained throughout the trial.

#### 6.2.3. Blinded Personnel

Participants, investigators, research midwives/nurses, laboratory outcome assessors and other attending clinicians will remain blind to the trial treatment allocation throughout the duration of the trial.

#### 6.2.4. Allocation Concealment

Given the randomisation methodology described above, allocation concealment will be maintained throughout the trial.

#### 6.2.5. Unblinding

Investigators will have access to unblinding in case of a medical emergency via the online code-break system or by contacting the LOCI Trial office.

Should any Serious Adverse Event occur, the management and care of the participant will be initiated as though the woman is taking metformin and either letrozole or clomifene. Cases that are considered serious, unexpected and possibly, probably or definitely related (please refer to section 9.6) will be unblinded only at the Trial Office by the LOCI Trial Manager (or other nominated individual), for reporting purposes. The attending clinician and local PI will not be made aware of the actual trial treatment unless it is deemed clinically necessary by the local clinical team.

In all other circumstances, investigators and research midwives/nurses will remain blind to treatment allocation whilst the participant remains in the trial. However, if a participant is withdrawn from the trial and only if the treatment allocation is required for the continued medical management of the withdrawn participant, care providers should attempt to contact the LOCI Trial Office in the first instance or use the online LOCI code-break system. This online service will be available 24 hours a day, seven days a week and will facilitate rapid unblinding. If they wish, participants may enquire and find out about their treatment allocation after the trial has ended by contacting the hospital or trial office directly.

**LOCI PROTOCOL** Sponsor's reference: RG\_18-272 v1.0 07-Nov-2019 Page 25 of 57 IRAS ID: 257918 EudraCT number: 2018-004641-16 ISRCTN: TBC

#### 6.2.6. Randomisation Process

Immediately after all eligibility criteria have been confirmed, consent has been obtained and baseline prognostic factors gathered, the participant can be randomised into the trial. Participants will be randomised into the trial by a secure online randomisation system which is available via the MedSciNet Clinical Trial Framework.

Each participating centre and each authorised member of the research team will be provided with a unique log-in username and password for this purpose. Online randomisation will be available 24 hours a day, seven days a week apart from short periods of scheduled maintenance. As a back-up, authorised members of the research team will be able to call the toll-free randomisation service ([name]). Telephone randomisations will be available Monday to Friday, between 09:00 and 17:00, except for bank holidays and University of Birmingham closed days.

Randomisation Notepads (a sample document is available separately) will be provided to investigators and may be used to collate the necessary information prior to randomisation. All the questions and data items on the Randomisation Notepad must be answered before a trial number and pack number may be given. If some data items are missing, randomisation will be suspended but may be resumed once the information is available. Only when all the eligibility criteria and baseline data items have been provided, will the trial and pack numbers be given and a confirmatory email sent to the randomising investigator, the local PI and the research midwife/nurse.

The trial number will be linked to a treatment pack number that will be available in the local hospital pharmacy, and the pharmacy will also receive notification of the randomisation by email.

## 6.2.7. Randomisation Records

Following randomisation, a confirmatory e-mail will be sent to the randomiser, local research nurse, local PI, local pharmacist and the trial office ([contact]).

Investigators will keep their own study file log which links participants with their allocated trial number in the LOCI Participant Recruitment and Identification Log. The Investigator must maintain this document, which is not for submission to the Trials Office. The Investigator will also keep and maintain the LOCI Participant Screening/Enrolment Log which will be entered into the trial database and kept in the Investigator Site File (ISF), and will be available to the Trials Office at all times. The LOCI Participant Recruitment and Identification Log and LOCI Participant Screening/Enrolment Log should be held in strict confidence.

# **6.3.** Informing Other Parties

If the participant has agreed, the participant's GP should be notified that they are in LOCI trial, using the LOCI GP Letter.

**LOCI PROTOCOL** Sponsor's reference: RG\_18-272 v1.0 07-Nov-2019 Page 26 of 57 IRAS ID: 257918 EudraCT number: 2018-004641-16 ISRCTN: TBC

# 7. TRIAL TREATMENT / INTERVENTION

# 7.1. Patient pathway

Randomisation into the trial will be considered the first visit (Visit 1) in the trial. Subsequent visits will depend on whether the participant has become pregnant. At this first visit, baseline medical details will be collected by staff prior to ovulation induction (OI) lasting up to six months. Participants will also be given a treatment diary to complete during the trial.

Should pregnancy be confirmed, participants will be advised to contact the trial team and arrange for Visit 2. At six months, if the participant has not contacted the research team, a member of the site team will call the participant to determine whether they have become pregnant. If a pregnancy is confirmed, Visit 2 may be booked at this point. Visit 2 is only for participants who have become pregnant. They will be asked to return any unused OI drugs and collect additional Metformin/placebo supply to last until 14 weeks gestation.

For participants who have not become pregnant by the end of the six months, the compliance assessment and end of study forms should be completed. Participants may return unused drugs at their next routine fertility clinic appointment.

Please see Figure 7 for an illustration of the participant pathway.

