## 8.2. Schedule of Assessments

			From randomisation							
Visit	Screening before clinic	Baseline clinic	Month 1	Month 2	Month 3	Month 4	Month 5	Month 6	Month 4-9*	Month 2-46**
Eligibility check	Х	х								
Valid informed consent		х								
Relevant medical history taken	х	х								
Concomitant medication		х	х	х	х	х	х	х	х	х
Randomisation		х								
Routine blood tests	Х	х								
D21 progesterone concentration blood test (where applicable)			х	х	х	х	х	х		
Dispensing of IMP		х								
Ultrasound monitoring of ovulation (optional, depending on local practice)			х							
Drug returns (participant visit)								χ†		
Phone call to participant								х	x #	
EQ-5D-5L questionnaires		х							х	х
11-14 week ultrasound scan (if participant becomes pregnant)									х	
Final outcomes (conception failure; pregnancy, antenatal, intrapartum, post-partum, Day 28 neonatal and										×
maternal outcomes)										

**Table 3.** Schedule of assessments. \*Exact month determined by when the participant becomes pregnant (e.g. if they become pregnant in month 1, subsequent assessments will be made in month 4). \*\*Exact month determined by when participant becomes pregnant, and if they miscarry or have a successful live birth. †Pregnancy to be confirmed by month 6, visit 2 scheduled accordingly. \*Second phone call to be made at week 15 of pregnancy.

**LOCI PROTOCOL** Sponsor's reference: RG\_18-272 v1.0 07-Nov-2019 Page 35 of 57

IRAS ID: 257918 EudraCT number: 2018-004641-16 ISRCTN: TBC

Relevant trial data will be transcribed directly into the web-based database. Source data will comprise the research clinic notes, hospital notes, hand-held pregnancy notes and laboratory results.

Women will be encouraged to report pregnancies and their outcome, any adverse events and any additional visits to non-participating hospitals to the research midwife. Self-reports will be verified against clinical notes by the research team.

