## 13.2.1. Primary Outcome Measure

The primary outcome is the proportion of women randomised who experience a live birth at and beyond 34 weeks of gestation. The denominator of this proportion will be all women randomised and the numerator will be those women who have conceived during the six ovulation induction cycles (maximum 240 days) and have gone on to have a live birth at or beyond 34 weeks. A log-binomial regression model will be used to calculate the adjusted relative risk and 95% confidence interval. Statistical significance of the treatment group parameter will be determined from the p-value generated by the model

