CRF: LOCI: 04. End of Ovulation Induction/Pregnancy Confirmation Form

Question:

Did the participant become pregnant within 240 days (8 months) of randomisation?' = Yes;

AND

 \circ 'If yes, date of positive pregnancy test:' = Use date

Time to pregnancy (weeks) = ((Date of positive pregnancy test)-(Randomisation Date))/7

• Number of ovulation induction cycles required for pregnancy

CRF: LOCI: 04. End of Ovulation Induction/Pregnancy Confirmation Form **Question:**

- \circ `Number of completed OI treatment cycles?'
- $\circ~$ 'Did the participant become pregnant within 240 days (8 months) of randomisation?' = Yes

Pregnancy end outcomes:

• Ongoing pregnancy at 12 weeks (range 11 to 14 weeks) of gestation

CRF: LOCI: 05. Pregnancy Booking Scan Form

Question:

 \circ `Did the woman undergo a booking scan at 11-14 weeks?' = Yes

AND

- \circ 'Gestation according to ultrasound scan:' = range 11 to 14 weeks
- 'Fetal heart beat present' = For each fetus

• Pregnancy loss (defined as pregnancy loss before 24 weeks of gestation)

CRF: LOCI: 07. Pregnancy Outcome Form

Question:

• 'Was the baby born alive?' = No;

AND

```
\circ 'Gestation at pregnancy end' = <24 weeks;
```

AND

 `If no, what was the pregnancy outcome:' = Miscarriage, Ectopic pregnancy, Molar pregnancy, Pregnancy of unknown location, Termination

• Twin live births

CRF: LOCI: 05. Pregnancy Booking Scan Form

Question:

 \circ 'Did the woman undergo a booking scan at 11-14 weeks?' = Yes

AND

• 'Fetal heart beat present' = For each fetus

AND

 \circ 'If more than 1 fetus, type of multiple pregnancy:' = List type

CRF: LOCI: 07. Pregnancy Outcome Form

Question:

CHECK FOR EACH FORM FOR EACH BABY

- \circ 'Was the baby born alive?' = Yes
- Gestational age at live birth

CRF: LOCI: 07. Pregnancy Outcome Form **Question:**

• 'Was the baby born alive?' = Yes

AND

• 'Gestation at pregnancy end:' = Use gestation

Where live birth ≥ 24 weeks:

```
Time from conception to delivery (gestational age)
•
CRF: LOCI: 07. Pregnancy Outcome Form
Question:
   \circ 'Was the baby born alive?' = Yes
AND
      'Gestation at pregnancy end:' = \geq24 weeks
   0
AND
     'Gestation at pregnancy end:' = Use Gestation
   0
   Gestational age <28/<32/<37 weeks
٠
CRF: LOCI: 07. Pregnancy Outcome Form
Question:
   \circ 'Was the baby born alive?' = Yes
AND
      'Gestation at pregnancy end:' = \geq24 weeks
   0
Categorise Gestational age at pregnancy end by: <28/<32/<37 weeks.

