Appendix C: Schedule of assessments

			From randomisation							
Visit	Screening before clinic	Baseline clinic	Month 1	Month 2	Month 3	Month 4	Month 5	Month 6	Month 4-9*	Month 2-18**
Eligibility check	х	х								
Valid informed consent		х								
Relevant medical history taken	x	х								
Concomitant medication		х	х	x	х	х	х	х	х	х
Randomisation		х								
Routine blood tests	x	х								
D21 progesterone concentration blood test (where applicable)			x	x	x	x	x	x		
Dispensing of IMP		х								
Ultrasound monitoring of ovulation (optional, depending on local practice)			x							
Drug returns (participant visit)								x†		
Phone call to participant								х	x#	
EQ-5D-5L questionnaires		x							х	х
11-14 week ultrasound scan (if participant becomes pregnant)									х	
Final outcomes (conception failure; pregnancy, antenatal, intrapartum, post- partum, Day 28 neonatal and maternal outcomes)										х

*Exact month determined by when the participant becomes pregnant (e.g. if they become pregnant in month 1, subsequent assessments will be made in month 4). **Exact month determined by when participant becomes pregnant, and if they miscarry or have a successful live birth. †Pregnancy to be confirmed by month 6, visit 2 scheduled accordingly. #Second phone call to be made at week 15 of pregnancy.

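### The active pregnancy check and study closure fall at six months, but the primary outcome counts conceptions up to day 240, so late conceptions depend on self-report.

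*Protocol*

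**What the plan says.** Protocol 7.1 describes treatment after the baseline visit as "prior to ovulation induction (OI) lasting up to six months". It then sets the one active status check for women who have not made contact: "At six months, if the participant has not contacted the research team, a member of the site team will call the participant". Closure follows at the same time: "For participants who have not become pregnant by the end of the six months, the compliance assessment and end of study forms" are completed.

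The footnote to the schedule of assessments (protocol Table 3, repeated in SAP Appendix C) agrees with this: "Pregnancy to be confirmed by month 6, visit 2 scheduled accordingly". The only later call in the schedule is for women who are already pregnant: "Second phone call to be made at week 15 of pregnancy".

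The outcome definition runs longer. Protocol 13.2.1 counts "those women who have conceived during the six ovulation induction cycles (maximum 240 days", and SAP 9.5 uses the same definition. SAP 9.4 takes pregnancy within the window from CRF 04, whose item reads "Did the participant become pregnant within 240 days (8 months) of randomisation?' = Yes".

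Neither document states when CRF 04 is completed, and neither gives a dated contact at or after day 240 for a woman not pregnant at six months.

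**The concern.** A woman still within her six cycles at six months can conceive afterwards and meet the primary outcome definition. If the pathway is followed as written, her end-of-study form has already been completed and nobody is scheduled to ask her again.

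If CRF 04 is completed at that same point, its 240-day item cannot yet be answered for her. A conception that she does not report could then be recorded as no live birth. That is a wrong value, not a missing one. The tipping-point analysis in SAP 9.10 alters only missing responses, so it would leave the error in place.

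The exposure is concentrated in women with long cycles, and cycles over 35 days are one of the routes to eligibility. If cycle length or duration of induction differed by treatment, the loss could also differ by arm; the documents give no figure for this. The comparison with least power to spare is letrozole plus metformin versus clomifene plus metformin, whose target was reduced from 90% to at least 80% in the February 2023 revision.

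**Working it through.** **Inputs.** Window: 240 days (protocol 13.2.1, SAP 9.4 and 9.5). Status check: six months, taken as 365.25/2 ≈ 183 days. Analysed numbers and rates (SAP 4.7, revised): 380 per arm at 44% vs 34% for letrozole plus metformin versus clomifene plus metformin; 760 per arm at 39% vs 29% for each main comparison. Alpha is 0.05, taken as two-sided because SAP 4.8 states a two-sided alternative.

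**Step 1: reproduce the plan's power.** Power = Φ[(d − 1.96·SE₀)/SE₁], with SE₀ from the pooled proportion and SE₁ from the separate proportions.
- 380 per arm, 44% vs 34%: SE₀ = 0.03539, SE₁ = 0.03520; (0.10 − 0.06935)/0.03520 = 0.871; power 80.8% (stated 81%).
- 760 per arm, 39% vs 29%: SE₀ = 0.02430, SE₁ = 0.02417; (0.10 − 0.04763)/0.02417 = 2.167; power 98.5% (stated 98.5%).

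**Step 2: the gap.** 240 − 183 = 57 days; 57/240 = 24% of the window.

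**Step 3: when the gap holds eligible cycles.** Conception must also fall within the six cycles. Run back to back from randomisation, six cycles end at:
- 28-day cycles: day 168, so none of the gap is used.
- 30-day cycles: day 180, none.
- 35-day cycles: day 210; 183/35 = 5.23 cycles elapsed at the check.
- 40-day cycles: day 240; 183/40 = 4.58 cycles elapsed.

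The break-even average is 183/6 ≈ 30.5 days, or longer than that only if treatment starts on time; a late first cycle would push even shorter cycles into the gap.

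**Step 4: illustrative loss.** The documents do not give the share of conceptions after six months, so this is a range. Assumptions: every woman has the stated cycle length, the chance is equal per cycle, part-cycles count pro rata, the plan's live birth rates serve as the rates at the end of the window, and there is no later report. The recorded rate is 1 − (1 − p)^x, where x is cycles elapsed divided by six.

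| Cycle length | x | 44% / 34% recorded as | Power | 39% / 29% recorded as | Power |
|---|---|---|---|---|---|
| ≤30 days | 1 | 44.0 / 34.0 | 81% | 39.0 / 29.0 | 98.5% |
| 35 days | 0.871 | 39.7 / 30.4 | 77% | 35.0 / 25.8 | 97.4% |
| 40 days | 0.7625 | 35.7 / 27.2 | 72% | 31.4 / 23.0 | 95.9% |

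In the first comparison, the relative loss is 9.8% and 10.7% of events at 35 days, and 18.8% and 20.1% at 40 days. In the main comparisons at 40 days it is 19.5% and 20.7%. Beyond 40 days the 240-day cap binds and x stays at 183/240 = 0.7625.

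**Step 5: partial self-report.** If half of the gap events in the 40-day case are later reported, the recorded rates are 39.9% vs 30.6% and 35.2% vs 26.0%. Power is then about 77% and 97.4%.

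**The case against.** A reader might infer that conceptions after six months have no planned ascertainment at all. The documents do not support that. Protocol 8.2 encourages women to report pregnancies, sets no time limit, and has self-reports verified against clinical notes. CRF 04 asks about the full 240 days, and its title ties it to the end of induction, not to month 6. The final-outcomes row, which includes conception failure, sits in a column running to month 46 (month 18 in SAP Appendix C). What is missing is a scheduled contact, not every route.

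A reader might also take the 72% as the expected power. It is the upper scenario: all women on 40-day or longer cycles and no late reports. The over-35-day criterion describes cycles before treatment and is only one of several alternative criteria; the documents give no treated-cycle length.

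It can further be argued that six months is shorthand for six cycles, since protocol 6.2.2 and Table 1 label cycles as months. This does not remove the conflict. The schedules count months from randomisation. The 240-day cap, and packs holding seven calendar months of metformin or placebo (protocol 7.7.2), show that treatment was expected to run past month 6.

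The version point stands. The protocol supplied is v1.0 and the SAP reflects later changes, so the current section 7.1 may differ. SAP Appendix C, however, still carries the month-6 footnote beside the 240-day definition.

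**Conclusion.** The timing conflict holds. The scheduled status check and closure for non-pregnant women precede the end of the primary outcome window by about 57 days, and no dated contact covers that interval. Ascertainment there is partial and passive. Whether an unreported late conception becomes a false non-event depends on when CRF 04 is completed, which is not stated.

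The size is unknown. It ranges from nothing, if cycles average about 30 days or less and start promptly, to roughly a fifth of events in the 40-day scenario with no later report. The main comparisons keep power above 95% throughout these scenarios; the letrozole plus metformin versus clomifene plus metformin comparison could fall below its 80% target. Pro rata counting is an approximation: counting completed cycles only would give a somewhat larger loss for long cycles, while self-report pulls every figure back towards the plan. Differential loss by arm is possible but cannot be quantified from the documents.

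**What to change.** Reconcile protocol 7.1, protocol Table 3 and SAP Appendix C with the 240-day window, leaving treatment duration untouched. For every woman not known to be pregnant, schedule the outcome status check at or after day 240, plus a short window for a positive test, and complete CRF 04 and the end-of-study form then. State that timing explicitly. The month-6 call can stay as an extra contact.

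For women already closed at six months, check records or re-contact them, within their consent, for conceptions up to day 240. Confirm first what the current section 7.1 says.

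The cost is wording changes, one later call per non-pregnant woman, and a records check or re-contact for those already closed. The last item is the larger part of the work if many women have finished follow-up.
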